### 7.5.3 Post-treatment follow-up; Vnnn

Patients will be followed [REDACTED]

At these [REDACTED] timepoints, which if the patient is unable to attend a site visit can be a telephone contact, the following will be done:

- survival status documentation (in case of death, an as precise as possible cause of death is going to be documented),
- documentation of safety; after the post-treatment visit for safety assessment (see [Section 7.5.1](#)) has been made, only SAEs with plausible causal relationship with trial treatment will be documented, and
- if applicable, collection of information regarding further anti-cancer treatments.

## 7.6 Safety assessments

Safety and tolerability of EO2401 in combination with nivolumab, the primary endpoint for the phase 1 part of the trial, will be assessed by a descriptive medical assessment of the combined profile of incidences of AEs, TEAEs, SAEs, deaths, reasons for treatment discontinuation/delays, and laboratory abnormalities. Adverse events will be categorized by their system organ class (SOC) and preferred term (PT) using the current MedDRA version and graded according to NCI-CTCAE v5.0 [\[60\]](#).

[figure not shown]
In addition, in the randomized extension of Cohort 2A safety and tolerability of EO2401/nivolumab will be assessed versus internal concurrent controls (groups of patients treated with EO2401 monotherapy and nivolumab monotherapy, respectively), by incidences of adverse events (AEs), treatment-emergent AEs (TEAEs), serious AEs (SAEs); AEs will be analyzed irrespective of relationship, and as related events.

The safety monitoring procedures of the trial are described in [Section 8](#), the specific parameters to monitor/assess are outlined in [Section 7.3](#), [Section 7.4](#), and [Section 7.5](#), and the timing of assessments also described in [Table 5](#).

Clinical laboratory analyses as described in [Section 7](#) will be performed by a local laboratory. More frequent evaluations may be performed at the Investigator's discretion if medically indicated; results of such evaluations should also be recorded in (e)CRFs. Normal ranges for all utilized local laboratories should be provided by the sites to the Sponsor.

## 7.7 Efficacy assessments

Computed tomography scans will be performed according to the Study Schedule [REDACTED] for assessments of tumor status; when adequate due to e.g. location of new metastatic disease, other examinations than CTs might be necessary for documentation of tumor status - such assessments are going to be done, and recorded in the trial documentation, on an individual patient basis based on the judgment of the Investigator. Tumor response and progression in this trial will primarily be evaluated by the investigators/local sites using the revised international criteria (1.1) proposed by the Response Evaluation Criteria in Solid Tumors (RECIST) committee [\[36\]](#) as well as the modified iRECIST guidelines [\[37\]](#); see [Section 12.1](#) for a further description of the criteria.

[figure not shown]

[figure not shown]
Investigators should especially note the different requirements for confirmatory scans as well as follow-up for the two criteria.

[figure not shown]
Of particular importance, in the context of confirmation of PD per iRECIST, and the given timeline of confirmatory scans to be performed at least 4 weeks, but no longer than 8 weeks after iUPD, is that in case of any signs of rapidly progressing disease establishment of PD and a following therapy switch should be made also earlier than 4-8 weeks after iUPD when necessary.

The main efficacy assessments will include ORR, DOR, PFS, and OS as outlined in [Section 3.2.2.](#)

[figure not shown]
The primary endpoint of the phase 2 part of the trial is the rate of patients without progression (according to iRECIST criteria [\[37\]](#)) or death due to any cause at 6 months after the first dose of randomized treatment. The primary endpoint is to be determined per investigator/local site assessments of progression. The denominator will be all patients who started the randomized treatment in Cohort 2A and will be determined for each randomized treatment group separately. Patients will be followed up for progression or death during the first 6 months after start of randomized treatment regardless of whether they stop treatment and continue on other regimens. Patients who are completely lost to follow-up will be counted as if they had a PFS event during the first 6 months.

A large black rectangular box used to redact sensitive information, covering the majority of the page below the text.

## 7.9 Assessments for other exploratory endpoints

A large black rectangular box used to redact the content of section 7.9.

## 8 SAFETY MONITORING

### 8.1 Safety monitoring definitions

#### 8.1.1 Adverse events

International Council for Harmonization (ICH) guideline E2A defines an AE as “any untoward medical occurrence in a patient or clinical investigation subject administered a pharmaceutical product and which does not necessarily have to have a causal relationship with this treatment”.

According to the FDA (21CFR312.32), an AE means any untoward medical occurrence associated with the use of a drug in humans, whether, or not, considered drug related.

*An AE can therefore be any unfavorable and unintended sign (e.g., tachycardia, enlarged liver), symptom (e.g., nausea, chest pain), abnormal result of an investigation (e.g., laboratory finding), or disease temporarily associated with the use of a medicinal product, whether or not considered related to the medicinal product.*

#### 8.1.2 Serious Adverse events

An SAE is any untoward medical occurrence that at any dose fulfills one or more of the following criteria:

- results in death,
- is immediately life-threatening,

*The term “life-threatening” in the definition of “serious” refers to an event in which the patient was at immediate risk of death at the time of the event; it does not refer to an event which hypothetically might have caused death if it were more severe.*

- results in persistent or significant disability/incapacity,

*Disability is defined as a substantial disruption in a person’s ability to conduct normal life functions (i.e. the AE resulted in a significant, persistent, or permanent change, impairment, damage, or disruption in the patient’s bodily function/structure, physical activities, or quality of life).*

- is a congenital anomaly/birth defect,
- requires inpatient hospitalization or prolongation of existing hospitalization, and

*A hospitalization is defined as an inpatient overnight stay, but this can be shorter than 24 hours.*

- is another medically significant event defined as an event that may not be immediately life-threatening or result in death or hospitalization but may jeopardize the patient or may require intervention to prevent any of the above listed outcomes.

#### 8.1.2.1 Excluded events

Hospitalization for the following reasons will not be regarded as serious (i.e. will not be immediately reportable):

- routine treatment or monitoring of the disease under study, including hospitalization due to trial-related procedures, not associated with any deterioration of the patient’s status,

- elective or pre-planned treatment (before signing the ICF) for a pre-existing condition that is unrelated to the disease under study and has not worsened since signing the ICF,
- treatment on an emergency outpatient basis for an event not fulfilling any of the definitions for an SAE and not resulting in hospital admission,
- underlying disease progression (the adrenal malignancy which is the basis for the patient enrollment in the trial) and events which are unequivocally (without doubt) related to the disease progression, and
- social reasons, respite care, and in the absence of a medical condition.

### ***8.1.3 Suspected Unexpected Serious Adverse Reactions (SUSARs)***

SUSARs are serious events that are not listed in the Reference Safety Information section of the EO2401 Investigator Brochure. Suspected adverse reaction means any AE for which there is a reasonable possibility that the drug caused the AE. For the purposes of Investigational New Drug safety reporting, “reasonable possibility” means there is evidence to suggest a causal relationship between the drug and the AE. In Europe, SUSARs will be reported as established in the EU Regulation No 536/2014.

When EO2401 is administered in combination with nivolumab, SUSARs are serious adverse events related to EO2401 that are not listed in the Reference Safety Information section of the EO2401 Investigator Brochure (i.e. all events, except local administration site reactions as described in the Investigator Brochure) and/or serious adverse events related to nivolumab that are not listed in the nivolumab European SmPC.

When nivolumab is administered alone, SUSARs are serious adverse events related to nivolumab that are not listed in the nivolumab European SmPC.

### ***8.1.4 Severity/intensity versus seriousness***

[figure not shown]
ICH E2A: The term “severe” is often used to describe the intensity (severity) of a specific event (as mild, moderate, or severe myocardial infarction); the event itself, however, may be of a relatively minor medical significance (such as a severe headache). This is not the same as “serious”, which is based on patient/event outcome or action criteria usually associated with events that pose a threat to a patient’s life or functioning. Seriousness (not severity) serves as a guide for defining regulatory reporting obligations.

## **8.2 Pregnancies**

Patients who are fertile must use adequate birth control methods during the trial, from signing the ICF through 5 months after the last study treatment dose administered (see [Section 6.9.4](#)).

Pregnancy is not considered an AE unless it meets any criteria for becoming serious (see [Section 8.1.2](#)). However, it is the responsibility of the Investigator or their designee to report any pregnancy in a patient or the patient’s sexual partner that occurs during the study. All patients who become pregnant must immediately discontinue the study drug and be withdrawn from study treatment.

The Investigator should make every effort to follow the patient until completion of the pregnancy and provide the corresponding information by the mean of a SAE/Pregnancy form within 2 weeks from awareness (see [Section 8.5.3](#)). The Sponsor Safety Group will periodically request from the investigator targeted follow-up information using specific pregnancy follow-up forms. If the events during pregnancy and/or outcome of pregnancy

(i.e. complications regarding mother/baby) meet the criteria for classification of an SAE, the Investigator must follow the procedures for SAE reporting.

### 8.3 Safety monitoring periods

#### 8.3.1 Reporting

In patients exposed to study treatment, the following must be reported from the date of the patient's signing the ICF until 30 days after the final administration of study treatment:

- AEs regardless of their causal relationship to study treatment,
- SAEs without a plausible causal relationship to study treatment, and
- pregnancy of the patient.

SAEs with a plausible causal relationship to study treatment must be reported from the date of the patient's signing the ICF until indefinitely (regardless of the time elapsed from the final study treatment administration).

In addition, for consistency with nivolumab clinical trial protocols as advised by Bristol-Myers Squibb (marketing authorization holder for nivolumab), collect all non-serious adverse events (not only those deemed to be treatment-related) continuously during nivolumab treatment periods and for a minimum of 100 days following discontinuation of nivolumab treatment. The most conservative approach (longest follow-up) emanating from the two principles (30 days and specifics per above paragraph versus 100 days following discontinuation of nivolumab treatment) should be followed for nivolumab.

In patients not exposed to study treatment, the reporting period for AEs (including SAEs regardless of causal relationship) starts with signature of the ICF and ends:

- the date of the Investigators assessment of "screen failure"-status (see [Section 5.3.2](#)), or
- the date of the patient's consent withdrawal.

#### 8.3.2 Follow-up

The Investigator assesses at each visit (or more frequently, if necessary) if there are any changes in AE diagnosis, severity, suspected causal relationship to clinical trial medication/procedure, interventions required to treat the event, and AE outcome.

An AE causally not related to study treatment is monitored (followed-up) until resolution, stabilization (becoming a permanent condition), or end of the clinical trial. Clinically relevant laboratory abnormalities will be followed up until they return to normal or become stabilized (permanent condition).

Any AE with a plausible causal relationship to study treatment as well as all SAEs (regardless of their causal relationship) will be followed up until the event has resolved or stabilized (permanent condition).

Pregnancies will be monitored by the Investigator to determine the outcome, including spontaneous abortion or voluntary termination, birth details, and the presence or absence of any birth defects, congenital abnormalities, or maternal and newborn complications. Every infant should be followed up for 2 months after delivery.

### 8.4 Assessing adverse events

Information about adverse reactions (causally related events) already known for EO2401 monotherapy, or EO2401 in combination with nivolumab, can be found in the current

version of the EO2401 IB or will be communicated between IB updates in the form of “Dear-Investigator Letter”.

#### 8.4.1 Causality

The Investigator needs to assess the causal relationship of any AE in relation to the study treatment (see [Section 6](#)). In context of the intended study treatment, as composed of EO2401 [REDACTED] administered in combination with nivolumab, it is most of the times in principle not possible to make causality assessments for each component by itself (due to the nature of the combination treatment and the mode of action of the components).

In the rare instances an AE would appear [REDACTED] between the first injection of EO2401, and the first infusion of nivolumab, there might be the possibility to assess causality for some types of AEs in relation to EO2401 [REDACTED] without the nivolumab component. In addition, there might also be a possibility to assess causality for some types of AEs in relation to EO2401 [REDACTED], without the nivolumab component, in cases where nivolumab administrations have been terminated but treatment continues with EO2401 [REDACTED]. There will be a possibility in the eCRF to record AEs taking these specific circumstances into account. Otherwise, it is assumed that the causality assessment is in relation to the complete study treatment.

The causality assessment is based on the Investigator’s clinical judgment taking into consideration all relevant information available at the time of AE reporting including:

- temporal association of the event onset with administration of the medication,
- known type of reaction for the administered compounds,
- disappearance or abating of symptoms when the compound(s) is discontinued, or withheld,
- reappearance of symptoms when the compound is re-administered,
- event may or may not be caused by the patient’s health condition,
- presence of risks or factors not related to trial intervention that are known to be associated with the occurrence of the event.

Causal relationship of all AEs will be classified as follows:

- **Not suspected:** it is not plausible that the AE is caused by the medication(s) and a likely alternative explanation exists. *There is no reasonable possibility of a causal relationship.*
- **Suspected:** it is plausible that the AE is caused by the medication(s). *There is a reasonable possibility of a causal relationship.*

*For the purposes of safety reporting, ‘reasonable possibility’ means there is evidence to suggest a causal relationship between the medication(s) and the AE.*

#### 8.4.2 Severity/intensity

Severity or intensity of an AE should be assessed according to the NCI CTCAE v5.0 [[60](#)]; a grading scale is provided for AE terms displaying grades 1 through 5 with unique clinical descriptions of severity for each AE.

## 8.5 Reporting by the investigational site

### 8.5.1 Adverse events

Any AE (including SAEs), whether, or not considered to be causally related to the trial medication and regardless of its seriousness, must be reported (described and recorded) in the AE section of the patient's eCRF on an ongoing basis.

A pre-existing condition is a clinical condition (including a condition being treated) that is diagnosed before the patient signs the ICF and that is documented as part of the patient's medical history; any clinically significant worsening of a pre-existing condition constitutes an AE. Also, any recurrence of a pre-existing condition is an AE.

The questions concerning whether the condition existed before the start of the active phase of the study and whether it has increased in severity and/or frequency will be used to determine whether an event is a TEAE. An AE is considered to be treatment-emergent if it is not present when the active phase of the study begins and is not a chronic condition that is part of the patient's medical history, or it is present at the start of the active phase of the study or as part of the patient's medical history, but the severity or frequency increases during the active phase. The active phase of the study begins at the time of the first dose of the study drug. The active phase of the study ends 100 days after the last study drug administration [REDACTED]

A standardized question such as "Have you had any health problems since your last visit or since you were last questioned?" will be given by the Investigator or the investigational site personnel at each contact with the patient.

[figure not shown]
Progression of the underlying disease or an AE unequivocally (without doubt) related to the progression of the underlying disease, regardless of its outcome or seriousness criteria, does not need to be reported as an AE/SAE. However, the medical conditions and underlying diseases associated with disease progression needs to be captured on the AE eCRF page (as a non-serious AE). An SAE must be reported only if there are clinical symptoms/signs that cannot be without doubt associated with the progression of the underlying disease.

Whenever possible, a diagnosis rather than symptoms should be provided (e.g. anemia instead of low Hb).

Abnormal laboratory and other abnormal examinations (e.g. at physical examination) should not be reported as AEs, unless they are associated with clinical signs/symptoms, require medical intervention/therapy (e.g. transfusion due to low Hb), require a change in trial medication (e.g. temporary interruption of treatment, or definitive treatment discontinuation), or are otherwise considered clinically relevant by the Investigator. Clinically relevant laboratory, or examination abnormalities will be followed up until they return to normal or become stabilized (permanent condition).

If a clinically significant laboratory abnormality is a sign of a disease or syndrome (e.g. ALP and bilirubin 5 times the ULN associated with cholecystitis), only the diagnosis (i.e. cholecystitis) should be recorded on the AE eCRF page.

If a clinically significant laboratory abnormality is not a sign of a disease or syndrome, the abnormality itself should be recorded on the AE eCRF page, along with a descriptor indicating if the test result is above or below the normal range (e.g. "elevated potassium," as opposed to "abnormal potassium"). If the laboratory abnormality can be characterized by a precise clinical term per standard definitions, the clinical term should be recorded as the AE. For example, an elevated serum potassium level of 7.0 mEq/L should be recorded as "hyperkalemia."

Physical examination findings will be compared with the baseline status and any clinically significant change, as assessed by the Investigator, should be documented as an AE.

A surgical procedure is not an AE but a therapeutic measure for a condition that necessitates surgery. Therefore, the condition for which the surgery is required should be reported as an AE.

Any pre-planned surgery (i.e. planned before signature of the ICF) or other intervention permitted by the protocol and the condition leading to that measure are not AEs. In such cases, the underlying condition needs to be documented in the patient's medical history.

Death itself is an outcome of an event, which needs to be described and reported using medical terminology. Information about death will be captured on the respective eCRF page along with relevant details (date of death, immediate and underlying causes of death).

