## 3.2 Study endpoints

### 3.2.1 Primary endpoint

- ***The primary endpoint of the phase 1 part*** includes safety and tolerability of EO2401 in combination with nivolumab by a descriptive medical assessment of the combined profile of incidences of adverse events (AEs), treatment-emergent AEs (TEAEs), serious AEs (SAEs), deaths, reasons for treatment discontinuation/delays, and laboratory abnormalities using the NCI-CTCAE v5.0 grading system [60].
- ***The primary endpoint of the phase 2 part*** is the rate of patients without progression (according to iRECIST criteria [37]) or death due to any cause at 6 months after the first dose of randomized treatment. Six months after the first dose of randomized treatment will be determined for each patient and is dependent on the exact time point of evaluation of the CT investigation scheduled at week 25 (day 169). The primary endpoint is to be determined per investigator/local site assessments of progression. The denominator will be all patients who started the randomized treatment in Cohort 2A\* and will be determined for each randomized treatment group separately. Patients will be followed up for progression or death during the first 6 months after start of randomized treatment regardless of whether they stop treatment and continue on other regimens. Patients who

are completely lost to follow-up will be counted as if they had a PFS event during the first 6 months.

\* Cohort 2A = patients with ACC who had prior systemic therapy for established locally advanced or metastatic disease

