### ***8.5.2 Documenting in the eCRF***

The reported term should be a medical diagnosis or sign/symptom of the event, not a procedure. Each symptom in a constellation of symptoms should be listed separately if the Investigator has not made a preliminary/tentative summary diagnosis.

Fluctuations or re-occurrences of a condition, which are considered normal for the patient and are recorded in patient's eCRF medical history, do not need to be reported as an AE. However, if the condition deteriorates during the trial it needs to be captured as an AE.

If the same AE occurs repeatedly it must be assessed and documented separately each time, if there are "AE-free" time periods between the AEs.

If possible, each AE should be evaluated to determine:

- event term or a description of the AE in medical terms (not as reported by the patient),
- severity grade as assessed by the Investigator (1 - 5 per NCI CTCAE v5.0),
- its causal relationship to study treatment as assessed by the Investigator (suspected; not suspected),
- event duration, including onset date and end date,
- action taken with study treatments due to the reported event (no action taken; interruption of administrations; treatment permanently withdrawn; other),
- other action taken (no action taken; medication required; surgical intervention required; other),
- event seriousness (non-serious or serious AE),
- event outcome (resolved without sequelae, resolved with sequelae, not resolved, fatal, unknown), and
- disease progression-related event (yes, no).

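### Protocol 8.5.1 and 8.5.2 give opposite recording instructions for an unchanged re-occurrence of a pre-existing condition, so AE counts depend on which rule a site follows

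*Protocol*

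**What the plan says.** Protocol 8.5.1 defines a pre-existing condition as one "that is diagnosed before the patient signs the ICF and that is documented as part of the patient's medical history". It makes clinically significant worsening of such a condition an AE and then adds a second trigger: "Also, any recurrence of a pre-existing condition is an AE". Every AE, serious or not and related or not, "must be reported (described and recorded) in the AE section of the patient's eCRF on an ongoing basis".

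Protocol 8.5.2, on eCRF documentation, exempts a class of these events from AE reporting: "Fluctuations or re-occurrences of a condition, which are considered normal for the patient and are recorded in patient's eCRF medical history". The exemption has one limit: "However, if the condition deteriorates during the trial it needs to be captured as an AE".

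The TEAE definition in 8.5.1 covers a condition that is present at first dose or is in the history, "but the severity or frequency increases during the active phase". A chronic history condition that does not change is not treatment-emergent.

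The phase 1 primary endpoint (Protocol 3.2.1) is a descriptive assessment that includes "incidences of adverse events (AEs), treatment-emergent AEs (TEAEs), serious AEs (SAEs), deaths". AE, TEAE and SAE incidences are also the secondary safety endpoint of the randomized extension, assessed against the two monotherapy groups (Protocol 3.2.2).

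**The concern.** Two sites can each follow the protocol and record the same event differently. One cites 8.5.1 and enters an AE. The other cites 8.5.2 and enters nothing. The test that separates them is whether the re-occurrence is normal for that patient. No criterion is given for this, and staff who know the treatment apply it, because the trial is open-label.

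Recurring history items are plausible in this population. Protocol 1.1.1 reports hormone excess in about 50–60% of ACC patients and lists hypertension among the features. Protocol 1.1.2 lists hypertension, arrhythmia and hyperglycemia from catecholamine release in pheochromocytoma. At stake is whether AE and TEAE incidences mean the same thing across sites and cohorts.

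**Working it through.** No arithmetic applies: the documents give no figure for recurring conditions. The check sets the rules side by side and follows one event through to the tables.

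**Step 1: does 8.5.2 cover the same event as 8.5.1?** By the 8.5.1 definition, a pre-existing condition is already documented in the medical history. The history requirement in 8.5.2 is therefore met in nearly every case, and the judgement of normality is the only condition that does any work. Because 8.5.1 lists recurrence in addition to worsening, it also covers recurrence without worsening. The overlap is real.

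**Step 2: what does each rule require?** Take a history condition that recurs after first dose.

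| Re-occurrence | 8.5.1 | 8.5.2 |
|---|---|---|
| Greater severity | AE, record | AE, record (deterioration) |
| Same severity, same frequency | AE, record | May be omitted if considered normal |
| Same severity, higher frequency | AE, record; treatment-emergent by the frequency limb | Record if the rise is seen as abnormal or as deterioration; may be omitted if deterioration means severity only |

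Row 1 shows no conflict, row 2 is a plain conflict, and row 3 depends on an undefined word. Protocol 7.3 does not settle it. It asks for illnesses first occurring or detected on study, and for worsening of concomitant illness, and is silent on unchanged recurrence.

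**Step 3: which counts move in row 2?**

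- *Any AE:* counted if recorded, absent if omitted.
- *TEAE, protocol definition:* an unchanged chronic history condition is excluded either way. A non-chronic condition that is absent at first dose and then recurs meets the first limb of the definition, so it counts if recorded.
- *TEAE, SAP 7.11.2:* the SAP repeats the protocol definition and then lists three exclusions: onset too long after the last dose, patients not treated, and onset before first dose without a worse CTCAE grade. A recurrence that starts on treatment meets none of them, so it counts if recorded, even when the condition is chronic.

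**Step 4: can the analysis repair an omission?** The SAP's data review confirms AEs that programming has classed as not treatment-emergent. It works on recorded AEs only, so an omitted episode is not among them.

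**Step 5: where does it show?** Protocol 8.5.2 requires repeated AEs with AE-free intervals to be entered separately, and the SAP overview table gives numbers of events as well as patients. Event counts are therefore the most exposed. Patient percentages move only where the patient has no other AE in the same row, which points to individual preferred-term rows.

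**The case against.** The strongest reply is that 8.5.2 is a specific documentation rule qualifying a general definition, which is an ordinary way to read two sections. It is permissive and does not forbid reporting, and it keeps deterioration reportable. That narrows the point to unchanged re-occurrences and to the ambiguous frequency case. It does not remove it, because 8.5.1 allows no exception and there is no cross-reference or order of precedence.

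A reader might infer that 8.5.2 hides even a several-fold rise in episodes and so defeats the TEAE definition. The text does not support that. A marked rise over the patient's recorded pattern is not naturally normal, and it can be read as deterioration. Only a severity-only reading loses it.

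A reader might also divide one patient by a cohort size and quote a percentage-point shift. The groups are small (SAP 4.2 gives 2 to 26 per group, and Cohort 1 had 3), but the shift occurs only if that patient has no other AE in the row. Local administration-site reactions are the main anticipated EO2401 events, so many patients will already count in the overall AE row.

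Blood pressure, heart rate, laboratory values and concomitant medication are collected independently of AE reporting. Clinically significant examination changes must be entered as AEs, and a standard health question is asked at each contact. The SAP summarizes vital signs, laboratory grades and ECG shifts. These give partial parallel evidence, notably for hypertension and hyperglycemia. They do not restore AE records, and episodes between visits may leave no trace in them.

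Finally, uncontrolled hormone secretion in ACC and uncontrolled blood pressure in MPP are exclusion criteria, which should reduce the number of such episodes.

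**Conclusion.** The conflict holds for unchanged re-occurrences. Protocol 8.5.1 requires a record that 8.5.2 waives. It affects the all-AE count, and TEAE counts for non-chronic conditions or, under the SAP's listed exclusions, for any recurrence with onset on treatment. A missed rise in frequency is a further possibility, conditional on a severity-only reading of deterioration.

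The size cannot be computed, because the number of patients with recurring conditions and the rule that sites actually followed are not in the documents. The endpoint is descriptive, so no error rate, power or sample size changes. The effect is on event counts, on individual preferred-term rows, and on comparability between sites and cohorts. It is worth correcting because the remedy is cheap and removes an open-label discretionary filter. It does not threaten the overall safety assessment.

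**What to change.** Make the two passages one reporting rule that uses the TEAE test.

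- In 8.5.2, write: *A re-occurrence need not be reported only if neither its severity nor its frequency exceeds the pre-study pattern recorded in the medical history; otherwise it is an AE.*
- In 8.5.1, replace the sentence on recurrence with a reference to that rule.
- For patients already treated (70 according to the Protocol synopsis), query recurring medical-history items before database lock. Limit the query to episodes documented in source records, because asking for recall would produce uneven ascertainment.
- In the study report, state which rule sites had applied. If the database is already locked, this statement is the part that can still be done.

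The cost is two protocol sentences, an eCRF completion note and one limited query round. The downside is a few more low-grade AEs on record.
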